For each cohort of 3 subjects in the continuous and intermittent administration approaches, dose escalation to the next higher dose may proceed if no dose-limiting toxicity (DLT) is observed within the first cycle of the 3 subjects accrued to a cohort. If 1 of 3 subjects in the cohort experiences a DLT, up to a total of 6 subjects will be enrolled. If 2 or more of the 3-6 subjects in a cohort experience a DLT, dose escalation will cease, and additional subjects will be treated at a lower dose level or with another schedule. If de-escalation to the previous dose cohort is undertaken, this cohort will be expanded to ≥6 subjects. Additional subjects (up to 12 total per cohort) may be evaluated to refine the estimation of the MTD and RP2D at the planned dose levels or at an intermediate dose level between the highest previously tolerated total dose and the next planned total daily dose. The MTD is defined as the highest dose at which < 33% of subjects experiences a DLT in the total dose and schedule cohort. The investigators and sponsor will review available data including toxicity, PK and antitumor activity data to reach consensus on dose levels and determination of the MTDs with continuous and intermittent dosing.

Once the MTD and/or recommended phase 2 dose (RP2D and schedule is determined, the study will enter the expansion stage (Stage 2), in which cohorts of subjects will be accrued in order to obtain additional information on safety, tolerability, preliminary anti-tumor activity, PK, and pharmacodynamic data at the RP2D and schedule when LAM-002A is administered alone or in combination with rituximab/rituximab hyaluronidase human or atezolizumab. Expansion-stage cohorts will comprise groups of subjects with specific types of previously treated, relapsed, progressive, and measurable NHL who will receive LAM-002A monotherapy or LAM-002A-containing combination therapy as shown in Table S-2. For both monotherapy and combination cohorts, the starting dose of LAM-002A will be 125 mg BID administered continuously.

Table S-2. Expansion Stage Disease Types and Therapies

Table 8-2. Expansion Stage Disease Types and Therapies						
Cohort Number	NHL Type	Investigational Regimen	Combination Drug	Evaluable Subjects, n		
1	FL	LAM-002A		Up to ~20		
2	MZL	LAM-002A		6		
3	DLBCL-GCB	LAM-002A		6		
4	DLBCL-ABC	LAM-002A		6		
5	FL or MZL	LAM-002A	Rituximab or rituximab hyaluronidase human	Up to ~20 with FL		

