6.1.2. Expansion Stage (Stage 2)

Once the MTD and/or recommended phase 2 dose (RP2D) and schedule is determined, the study will enter the expansion stage, in which cohorts of subjects will be accrued in order to obtain additional information on safety, tolerability, preliminary anti-tumor activity, PK, and pharmacodynamic data at the RP2D and schedule when LAM-002A is administered alone or in combination with rituximab/rituximab hyaluronidase or atezolizumab. Expansion-stage cohorts will comprise groups of subjects with specific types of previously treated, relapsed, progressive, and measurable NHL who will receive LAM-002A monotherapy or LAM-002A-containing combination therapy as shown in Table 2. For both monotherapy and combination cohorts, the starting dose of LAM-002A will be 125 mg BID administered continuously.

Version 9, 18 Feb 2020

Table 2: Expansion Stage Disease Types and Therapies

Cohort Number	NHL Type	Investigational Drug	Combination Drug	Evaluable Subjects, n
1	FL	LAM-002A		Up to ~20
2	MZL	LAM-002A		6
3	DLBCL-GCB	LAM-002A		6
4	DLBCL-ABC	LAM-002A		6
5	FL or MZL	LAM-002A	Rituximab or rituximab hyaluronidase human	Up to ∼20 with FL
6	DLBCL-GCB or DLBCL-ABC	LAM-002A	Rituximab or rituximab hyaluronidase human	6
7	FL or MZL	LAM-002A	Atezolizumab	6
8	DLBCL-GCB or DLBCL-ABC	LAM-002A	Atezolizumab	6

Abbreviations: ABC: activated B-cell (subtype); DLBCL: diffuse large B-cell lymphoma; FL: follicular lymphoma; GCB: germinal center B-cell (subtype); MZL: marginal zone lymphoma; NHL: non-Hodgkin lymphoma

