6.1.4. Subject Allocation (Stage 1 and Stage 2)

Subjects will be allocated to the cohorts by the study sponsor working in collaboration with each investigator considering the availability of openings for enrollment in Stage 1 or 2, disease type (i.e., FL, MZL, DLBCL-GCB, DLBCL-ABC, or other indications), therapy history (e.g., prior use of anti-CD20 or anti-PD1/PDL1 antibodies), and current disease status (e.g., potential to benefit from rituximab treatment based on past responses to anti-CD20 antibody therapy).

During Stage 1 dose ranging with LAM-002A monotherapy, allocation will be performed according to a 3+3 dose-escalation procedure with the requirement that each cohort of 3 subjects be observed for ≥4 weeks before another cohort is enrolled (as detailed in Section 6.6). During Stage 2 cohort expansion evaluating LAM-002A monotherapy, allocation will be performed as subjects present to the accruing clinics and there will be no specific restrictions on the cadence of enrollment. During Stage 2 cohort-expansion of LAM-002A combinations with rituximab and

Version 9, 18 Feb 2020

atezolizumab, enrollment of the first 3 subjects in each combination cohort will be restricted such that each subject must be enrolled sequentially and observed for \geq 3 weeks before the next subject is enrolled. Beginning with the 4th patient in each combination group, further enrollment may proceed without restriction as long as the continuous reassessment boundaries for toxic drug discontinuations are not met (as detailed in Section 6.8.4.4 and Section 14.1.2).

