As noted above, the target ORR with LAM-002A alone is ~40%. Adding rituximab or rituximab hyaluronidase human to LAM-002A would be expected to enhance the ORR over that associated with single-agent LAM-002A. Thus, the combination of LAM-002A/rituximab could warrant further development if an ORR of \geq 60% could be targeted in preference to an ORR of < 40%. Accordingly, for combination therapy, sequential boundaries will be used to continuously monitor that the ORR is \geq 60% while excluding an ORR of 39% using a 1-sided test with a significance level of 0.05. A significant result with this testing would conclude with 95% confidence that the actual ORR is > 39%. Accrual of up to \sim 20 evaluable subjects will be considered with the potential to stop accrual early if the boundary is crossed. Thus, accrual can be considered sufficient if the following n/N values are observed: 7/10, 8/11, 8/12, 9/13, 9/14, 10/15, 10/16, 11/17, 11/18, 12/19, 12/20. For all these values, the ORR is \geq 60% with a lower 1-sided binomial confidence bound of \geq 39%.

Experience indicates the rates of discontinuations from rituximab or atezolizumab therapy are < 5% (Genentech 2016, Genentech 2017). A rate of AE discontinuations of therapy due to adverse events of \geq 25% in the 2 combination therapy groups of LAM-002A/rituximab (N = 12) or LAM-002A/atezolizumab (N = 12) would suggest a potential adverse interaction among the components of the combination therapy. Sequential Pocock-type boundaries will be used to continuously monitor the rate of AE discontinuations and to test the null hypothesis, after each subject, that the event rate is \geq 0.25 using a 1-sided significance test of \sim 0.05. AE discontinuation rates will be considered excessive if the following n/N values are observed: -/1, -/2, 3/3, 3/4, 4/5, 4/6, 5/7, 5/8, 5/9, 6/10, 6/11, 7/12. With this method, the probability of detecting an AE discontinuation safety signal ranges from 0.091 to >0.820 for true discontinuation rates of 25% to \geq 60%. If excessive levels of AE discontinuation are observed, the sponsor, working in collaboration with the cooperating companies and investigators, will take appropriate actions (eg, continuation of the cohort with modifications in design or monitoring plan, interruption of cohort accrual, cohort therapy discontinuation).

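### The AE-discontinuation boundary for LAM-002A/rituximab is written for 12 subjects and ends at 7/12, but the plan allows up to about 26 evaluable subjects on that combination

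*Combined protocol and SAP*

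**What the plan says.** Section 14.1.2, and the matching part of the synopsis, treats an AE-discontinuation rate of 25% or more as a possible sign of an adverse interaction "in the 2 combination therapy groups of LAM-002A/rituximab (N = 12) or LAM-002A/atezolizumab (N = 12". Pocock-type boundaries are applied after each subject at a one-sided level of about 0.05 against a reference rate of 0.25. No count is flagged for the first two subjects; after that the flagged counts are "3/3, 3/4, 4/5, 4/6, 5/7, 5/8, 5/9, 6/10, 6/11, 7/12". The stated probability of a signal is 0.091 at a true rate of 25% and above 0.820 at 60% or more.

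Table 2 (Section 6.1.2) and Table S-2 give the size of cohort 5, FL or marginal zone lymphoma (MZL) with rituximab, as "Up to ∼20 with FL". Cohort 6, diffuse large B-cell lymphoma (DLBCL) with rituximab, has 6.

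Section 6.1.4 staggers the first three subjects of each combination cohort. From the fourth patient in each combination group, "further enrollment may proceed without restriction as long as the continuous reassessment boundaries for toxic drug discontinuations are not met". It refers the reader to Sections 6.8.4.4 and 14.1.2 for these boundaries.

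**The concern.** The monitoring rule and the accrual plan for the same combination use different group sizes. N = 12 fits two cohorts of 6. It still fits atezolizumab (cohorts 7 and 8, 6 + 6 = 12), but not rituximab, where cohort 5 now runs to about 20 FL subjects. Section 14.1.2 carries the response boundary for those FL subjects to 12/20, and the next paragraph leaves the discontinuation boundary at 12 subjects. No reason is given for ending it there, so it looks like a value missed when FL accrual was expanded (the amendment summary dates that to Amendment 7).

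Two things are at stake. First, the enrolment condition in Section 6.1.4 has no content after subject 12, because no count exists that could meet the boundary. Second, the stated detection probabilities describe only the first 12 subjects, and a reader could take them as describing the whole group.

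**Working it through.** **Inputs.** Boundary values, reference rate 0.25, N = 12 and stated probabilities: Section 14.1.2. Cohort sizes: Table 2. Stage 2 total of about 76: Section 6.2. FL accrual on rituximab may be judged sufficient from 7/10: Section 14.1.2.

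**1. Reproduce the plan's figures.** Let P(n, k) be the probability of k discontinuations among n subjects with no crossing so far, and p the true rate. Then

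P(n, k) = (1 − p) · P(n − 1, k) + p · P(n − 1, k − 1),

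and any mass at or above the listed count for n is removed and added to the crossing probability. Over n = 1 to 12:

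| True rate | Crossing probability by subject 12 | Stated |
|---|---|---|
| 25% | 0.0908 | 0.091 |
| 40% | 0.364 | – |
| 50% | 0.609 | – |
| 60% | 0.8201 | >0.820 |

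Both stated figures reproduce, so they are properties of a 12-subject rule.

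**2. Planned size of the rituximab group.** 20 + 6 = 26 evaluable. As a check, the eight cohorts sum to 20 + 6 + 6 + 6 + 20 + 6 + 6 + 6 = 76, which matches Section 6.2.

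**3. Share beyond the last boundary value.** (FL + 6 − 12) / (FL + 6):

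| FL subjects in cohort 5 | Group size | After subject 12 | Share |
|---|---|---|---|
| 10 (stop at 7/10) | 16 | 4 | 25% |
| 14 | 20 | 8 | 40% |
| 18 | 24 | 12 | 50% |
| 20 | 26 | 14 | 54% |

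If N = 12 were read as applying to cohort 5 alone, (20 − 12)/20 = 40% would still lie beyond it.

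**4. What an extension would do (illustration only).** Keep all listed values. From subject 13, take the smallest count r for which P(X ≥ r), with X binomial (n, 0.25), is at most 0.0508, the largest such tail among the listed values (3/4). This gives 7/13, 7/14, 8/15, 8/16, 8/17, 9/18, 9/19, 9/20, 10/21, 10/22, 10/23, 11/24, 11/25, 11/26. The same recursion gives:

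| True rate | Present rule, 12 subjects | Extended, 26 subjects |
|---|---|---|
| 25% | 0.091 | 0.130 |
| 40% | 0.364 | 0.615 |
| 50% | 0.609 | 0.892 |
| 60% | 0.820 | 0.987 |

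**5. Cross-reference.** Section 6.8.4.4 covers atezolizumab dose modification and supportive care. It contains no boundary.

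**The case against.** Four points can be made for the plan.

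- **The figure of 26 is a ceiling.** A reader might infer that at least 26 subjects will be treated and that more than half are always uncovered. The documents say up to about 20 with FL, allow FL accrual to stop from 7/10, and give monotherapy enrolment preference. MZL or non-evaluable subjects could raise the treated number, but no minimum is set. "Over half" needs more than 24 subjects in the group. This limits the size of the point; the mismatch remains, because every listed FL stopping point plus 6 DLBCL subjects exceeds 12.
- **Safety monitoring does not stop.** A reader might infer that the combination loses its safety oversight. It does not: AEs are assessed at every scheduled visit (Section 8.5), SAEs and AEs of special interest are reported within 24 hours and reviewed by the medical monitor (Section 10.6), and rituximab has its own interruption and discontinuation table (Section 6.8.3.4). Nor is crossing the boundary a hard stop, since Section 14.1.2 lists continuing the cohort with modifications among the responses. What ends is the one pre-specified discontinuation rule.
- **The SAP may differ.** Section 14.2 lets the SAP modify the protocol's plans, and only part 1 of the document was available here. That would not correct the N = 12 printed in the protocol, on which Section 6.1.4 relies.
- **Accrual may be largely over.** Version 9 adds an extension stage for at most 4 continuing subjects, which suggests that Stage 2 was near its end but does not establish it. The text still sets out Stage 2 enrolment as open.

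It is also tempting to measure the defect against a rule built on a 5% tolerated rate. The documents give below 5% as experience with rituximab or atezolizumab, not as a tolerated rate for the combination. Such a rule (flag at 2 events among 2–5 subjects, 3 among 6–13, 4 among 14–22, 5 among 23–26) detects a true rate of 25% with probability 0.89 over 26 subjects, but already 0.64 if cut off at 12. Most of the gain over 0.091 therefore comes from changing the reference rate, not from covering later subjects.

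**Conclusion.** Wrong as written. The N of 12 for LAM-002A/rituximab conflicts with Table 2, Table S-2 and the Stage 2 total, all of which imply up to about 26 evaluable subjects. Up to 14 of 26 (54%), or 4 of 16 (25%) if FL accrual stops at 7/10, would have no pre-specified AE-discontinuation boundary, although Section 6.1.4 makes their enrolment conditional on one. The stated 0.091 and >0.820 are correct for 12 subjects and say nothing about later ones. The atezolizumab group is not affected.

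These counts take FL plus DLBCL evaluable subjects only, assume cohort 6 fills, and pool cohorts 5 and 6 as one group, as the N of 12 implies. The crossing probabilities assume independent subjects with a constant discontinuation rate.

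**What to change.** 1. In Section 14.1.2 and the synopsis, reconcile N for LAM-002A/rituximab with Table 2, and say whether MZL and non-evaluable subjects count towards it.
2. Extend the boundary to the planned maximum without loosening the values for subjects 1 to 12. Re-deriving the whole table at a tighter overall error could do that. For example, a 26-subject table against the same 25% rate that starts at 4/4 and needs 5 events at 5–7 subjects, 6 at 8–9 and 7 at 10–12 lowers detection within the first 12 subjects from 0.609 to 0.432 at a true rate of 50%.
3. Restate the operating characteristics for the extended rule. The continuation shown in the working is one option, not a recommendation; the reference rate remains the sponsor's choice.
4. In Section 6.1.4, correct the reference to Section 6.8.4.4.

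The cost is protocol wording and one table, since AEs leading to discontinuation are already recorded. The statistical price of that continuation is a somewhat higher chance of a signal at a true rate of 25% (0.130 against 0.091).

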14.1.3. Extension Stage (Stage 3)

The sample size in the extension stage of the study will be no higher than the total number of subjects on study therapy on the data cutoff date that concludes the dose-escalation and expansion stages of the clinical trial.

14.2. Statistical and Analytical Plans

Detailed methodology for summary and statistical analyses of the data collected in this trial will be documented in a statistical analysis plan (SAP). The SAP may modify the plans outlined in the protocol; any major modifications of the primary endpoint definition and/or its analysis will be described in the SAP and the final clinical study report. Additional statistical analyses other

Version 9, 18 Feb 2020

than those described in this section may be performed if deemed appropriate and will be described in the SAP. Where individual data points are missing because of insufficient samples, dropouts, or other reasons, the data will be analyzed based on reduced denominators.

Results will be summarized by dose cohorts.

14.3. Analysis Sets

14.3.1. Full Analysis Set

The full analysis set includes all subjects who receive ≥ 1 dose of study drug. This analysis set will be used in the analyses of subject characteristics, study drug administration and compliance, safety, and categorical and time-to-event efficacy outcomes. In analyses of response rates in the full analysis set, subjects who do not have sufficient baseline and on-study tumor assessments to characterize response (i.e., have a best overall response of NE) will be counted as failures.

14.3.2. Responding Analysis Set

The responding analysis set includes subjects in the full analysis set who have measurable disease, who can be evaluated for tumor response with both baseline and on-study tumor evaluations, and who achieve a CR, CRi, or PR. This analysis set will be used in the analyses of time to response and duration of response.

14.3.3. Evaluable Analysis Sets

The evaluable analysis sets include subjects in the full analysis set who have the necessary baseline and on-study measurements to provide interpretable results for specific parameters of interest. These analysis sets will be used in the analyses of changes in tumor dimensions, PK parameters, and pharmacodynamic parameters.

14.4. Demographics and Baseline Disease Characteristics

Demographics and other baseline characteristics will be summarized by dose escalation cohorts and expanded cohorts.

14.5. Study Drug Exposure

Study drug exposure information will be summarized using descriptive statistics such as number of treatment cycles and total dose.

14.6. Concomitant Medications

Medications under use at the time of or initiated after enrollment will be summarized by cohorts.

14.7. Safety and Tolerability

Safety and tolerability of LAM-002A will be assessed based on the following:

• Incidence, severity of treatment-emergent AEs, SAEs, AEs resulting in permanent discontinuation of study drug, and deaths on treatment through approximately 30 days from

Version 9, 18 Feb 2020

the last dose of study drug (or immediately before the administration of another anti-cancer treatment)

- Changes in laboratory test results
- Changes in vital signs including blood pressure, pulse, and temperature
- Changes in electrocardiogram results

Adverse events will be coded using the latest available version of the Medical Dictionary for Regulatory Activities (MedDRA). Treatment-emergent AEs are defined as AEs that start on or after the first dose of study drug and within approximately 30 days of the last administration of study drug. Adverse events will be summarized by the number and percentage of subjects who experienced the event, according to system organ class and preferred term. A subject reporting multiple cases of the same AE will be counted once within each system organ class and similarly counted once within each preferred term.

Unless specified otherwise, the denominator for these calculations will be based on the number of subjects in each cohort who received at least one administration of LAM-002A irrespective of the total number of doses or treatment cycles administered. These conventions will be appropriately modified to calculate AE incidence rates separately for each cycle that study therapy is administered.

AEs will also be summarized by NCI-CTCAE Version 4.0 severity grade and by relationship to each study drug. Additional summaries may also be provided for SAEs, and events resulting in the permanent discontinuation of therapy. All AEs will be included in individual subject listings.

The changes in hematology, chemistry, and other laboratory values will be summarized descriptively for each scheduled and unscheduled protocol assessment time point. Changes will be calculated relative to the values collected at baseline and on the first day of each cycle of treatment.

The incidence of DLT will be provided by treatment cycle and across all treatment cycles. The toxicity grades for laboratory tests will be based on NCI-CTCAE Version 4.0 criteria. Subject listings of all laboratory data collected during the study will be presented. Laboratory values outside normal limits will be identified in the subject listings and will include flags for high and low values.

Vital sign results (blood pressure, pulse, respirations, and temperature) will be summarized descriptively for each scheduled and unscheduled protocol time point. Changes will be calculated relative to the assessments at baseline and on the first day of each cycle of therapy.

14.8. Biomarkers

Descriptive statistics will be primarily used to summarize the biomarker and other laboratory data generated in this study. For continuous variables, the number of subjects with non-missing data, mean, either the standard error or standard deviation, median, 25th percentile (first quartile), 75th percentile (third quartile), minimum, and maximum will be presented. For discrete data, the frequency and percent distribution will be presented.

Version 9, 18 Feb 2020

The Wilcoxon signed rank test may be used to identify any statistically significant (p < 0.05) changes in biomarker levels. Additionally, correlations may be assessed by calculating Spearman's correlation coefficient between pairs of biomarkers or other parameters.

14.9. Efficacy Analysis

The tumor response will be assessed by the modified criteria for NHL (Cheson 2014) and revised guidelines for the diagnosis and treatment of CLL (Hallek 2008, Cheson 2012) (see Appendix 2).

The objective response rate will be estimated for each dose escalation cohort and each expanded cohort. The estimate of the objective response rate will be calculated based on the maximum likelihood estimator (i.e., crude proportion of subjects whose best overall response is CR or partial remission [PR]). The estimate of the objective response rate will be accompanied by 2-sided 95% exact binomial confidence intervals.

The duration of objective response will be calculated for subjects who achieve CR or PR. For such subjects, the duration of objective response is defined as the number of days from the start date of PR or CR (whichever response is achieved first) to the first date that progressive disease is objectively documented. The duration of objective response will be right-censored for subjects who achieve CR or PR and meet 1 of the following conditions: 1) non-protocol anticancer treatment started before documentation of disease progression, 2) death or documented disease progression after more than 1 missed disease assessment visit, or 3) alive and does not have documentation of disease progression before a data analysis cutoff date.

The duration of objective response will be summarized descriptively using the Kaplan-Meier method. The 50th percentile of the Kaplan-Meier distribution will be used to estimate the median response duration.

Progression-free survival (PFS) will be measured as from the date of enrollment to the date of documented progression or death (whatever the cause). Subjects who are alive and progression free at last follow-up (up to a year from first treatment at Cycle 1 day 1) will be censored. Those who start another anticancer treatment without evidence of progression will be censored at start date of the new therapy.

The PFS will be summarized descriptively using the Kaplan-Meier method. The 50th percentile of the Kaplan-Meier distribution will be used to estimate the median PFS of each cohort of subjects.

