14.1.2. Cohort Expansion Stage (Stage 2)

As indicated in Section 6.1.2, expansion cohorts of 6 subjects will be accrued. Enrollment of 6 subjects per cohort offers the opportunity to determine if there is any antitumor activity sufficient to warrant further development in the selected tumor types. An ORR of \geq 35% is considered of potential interest in each of the selected indications. If 0/6 subjects in a cohort experience an objective response, then a population ORR of \geq 35% for that cancer can be excluded with > 90% certainty (1-sided exact binomial 90% CI upper bound = 32%).

Based on the observation of objective responses among study subjects with FL receiving either LAM-002A monotherapy or LAM-002A/rituximab, expanded accrual of subjects with relapsed FL is planned to evaluate the level of activity with these 2 regimens. Preference will be given to enrolling subjects to receive LAM-002A monotherapy before enrolling subjects to receive LAM-002A/rituximab.

Based on historical data with other treatments (Zelenetz 2014), it is known that an ORR of < 20% in subjects with relapsed FL receiving LAM-002A monotherapy would be uninteresting while achieving a target ORR of $\ge 40\%$ would suggest that further development is warranted. Sequential boundaries will be used to continuously monitor that the ORR is $\ge 40\%$ while

Version 9, 18 Feb 2020

excluding an ORR of < 20% using a 1-sided test with a significance level of 0.05. A significant result with this testing would conclude with 95% confidence that the actual ORR is \geq 20%. Accrual of up to ~20 evaluable subjects will be considered with the potential to stop accrual early if the boundary is crossed. Thus, accrual can be considered sufficient if the following n/N values are observed: 4/5, 4/6, 4/7, 5/8, 5/9, 5/10, 5/11, 6/11, 6/12, 6/13, 6/14, 7/15, 7/16, 7/17, 8/18, 8/19, 8/20. For all these values, the ORR is \geq 40% with a lower 1-sided binomial confidence bound of \geq 20%.

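### The two FL expansion cohorts may stop on a response boundary, but Section 14.9 reports their ORR with no allowance for stopping, and the 0.05 level in Section 14.1.2 holds per look only

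*Combined protocol and SAP*

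**What the plan says.** Section 14.1.2 (repeated in the synopsis) sets up continuous monitoring of ORR in FL subjects on monotherapy (Cohort 1) and on the rituximab combination (Cohort 5), "with the potential to stop accrual early if the boundary is crossed". The monotherapy rule aims at "excluding an ORR of < 20% using a 1-sided test with a significance level of 0.05", with a 40% target. Its stopping pairs are "4/5, 4/6, 4/7, 5/8, 5/9, 5/10, 5/11, 6/11, 6/12, 6/13, 6/14, 7/15, 7/16, 7/17, 8/18, 8/19, 8/20". The combination rule aims at "excluding an ORR of 39% using a 1-sided test with a significance level of 0.05", with a 60% target and eleven pairs from 7/10 to 12/20. The section says that crossing gives 95% confidence that the ORR is at least 20%, or above 39%.

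Section 14.9 covers each dose-escalation and expansion cohort alike: "The estimate of the objective response rate will be calculated based on the maximum likelihood estimator", that is, the crude proportion, with "2-sided 95% exact binomial confidence intervals". It makes no exception for the two monitored cohorts. Section 14.10 (Interim Analysis) deals only with dose escalation.

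The denominators also differ. Section 6.1.5 defines evaluable Stage 2 subjects, and the boundary counts these. Section 14.3.1 counts non-evaluable subjects as failures in the full analysis set. Table 2 admits FL or MZL to Cohort 5 but sets its target of about 20 for FL.

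**The concern.** A cohort that may stop when its response count is high tends to stop on a favourable run, and the crude proportion then carries that run into the report. The 40% and 60% targets are the stated grounds for further development, so any overstatement falls on the number that drives the decision, and mostly when the cohort succeeds. In addition, a 0.05 test applied at up to 16 successive looks (monotherapy) or 11 (combination) does not keep an overall error of 0.05. The confidence statement attached to crossing is therefore stronger than the design supports.

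**Working it through.** **Inputs.** Nulls of 20% and 39%, one-sided 0.05, targets of 40% and 60%, maximum N of 20, and both lists of pairs, all from Section 14.1.2. N = 11 appears twice in the monotherapy list (5/11 and 6/11). Results use 6/11; where 5/11 changes a figure, a range is given.

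**1. The plan's own bounds.** The fixed-N exact one-sided 95% lower bound L for x/N solves P(X ≥ x | N, L) = 0.05.
- Monotherapy: 16 of 17 pairs give L ≥ 20%. 5/11 gives 19.96%, which is 20% after rounding. 8/20 gives 21.7%.
- Combination: all 11 pairs give L ≥ 39%. 12/20 gives 39.4%.

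The stated bounds therefore reproduce, as single-look bounds.

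**2. Stopping distribution.** Let f_n(x) be the probability of having x responses in n subjects without having stopped. Then f_n(x) = f_{n-1}(x)(1 − p) + f_{n-1}(x − 1)p. Stop when x reaches the listed count, or at n = 20. As a check, the same recursion applied to the AE-discontinuation boundary gives 0.0908 at 25% and 0.8201 at 60%, matching the 0.091 and 0.820 in Section 14.1.2.

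**3. Overall error at the null.** The first monotherapy looks can be done by hand at p = 0.20:
- 4/5 or better: 5 × 0.2⁴ × 0.8 + 0.2⁵ = 0.0067
- first crossing at 4/6: 10 × 0.2³ × 0.8² × 0.2 = 0.0102
- first crossing at 4/7: 20 × 0.2³ × 0.8³ × 0.2 = 0.0164

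The sum by N = 7 is 0.0333. Carried to N = 20, the probability of crossing is 0.081 (0.087 with 5/11). For the combination at 39% it is 0.099.

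**4. Bias of the crude ORR, stopping at first crossing with no overrun.** E[x/n] is summed over the stopping distribution.

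| Cohort | True ORR | Mean crude ORR | Bias (points) | Mean given crossing |
|---|---|---|---|---|
| Monotherapy | 30% | 34.4% | +4.4 | 53.4% |
| Monotherapy | 40% | 46.8% | +6.8 | 55.5% |
| Combination | 50% | 52.7% | +2.7 | 68.5% |
| Combination | 60% | 63.4% | +3.4 | 70.4% |

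The probability of stopping before N = 20 at the target is about 65% (monotherapy) and 64% (combination).

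**5. Sensitivity to how stopping works in practice.** The protocol gives no figure for overrun, so the numbers of extra subjects are assumptions, with the total capped at 20.
- Subjects counted after crossing (2, 3, 5): bias +4.3, +3.5, +2.3 for monotherapy at 40%; +2.2, +1.8, +1.1 for the combination at 60%.
- First look at a later N, no overrun: monotherapy +5.4 from N = 7, +3.4 from N = 10, +2.4 from N = 12; combination +2.4 from N = 12.

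**6. Adjusted figures.** The stage-wise lower bound is the p at which the probability of a result at least as extreme equals 0.05, ranking earlier crossings as more extreme. The median-unbiased estimate uses 0.5 in place of 0.05.

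| Result | Crude | Median-unbiased | Fixed-N one-sided 95% bound | Planned two-sided 95% lower limit | Stage-wise one-sided 95% bound |
|---|---|---|---|---|---|
| 8/20 monotherapy | 40% | 34–35% | 21.7% | 19.1% | 17.3–17.7% |
| 12/20 combination | 60% | 54% | 39.4% | 36.1% | 34.8% |

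Some listed pairs cannot be a first crossing: 5/8, for example, requires 4/7 or better already. At the pairs that can be, the stage-wise bound is below 20% at 7 of 12 (monotherapy) and below 39% at 5 of 6 (combination).

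**7. Coverage.** Under the listed boundaries the planned two-sided 95% exact interval covers the true ORR with probability 0.962 to 0.990 at the rates tried.

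**The case against.** The best defence is that strict stopping is an upper-end scenario. Section 14.1.2 permits stopping rather than requiring it. Monotherapy enrolment has no pacing restriction (Section 6.1.4) and the first on-treatment scan comes around Cycle 3 Day 1 (Table 8), so more subjects may be enrolled before a crossing is seen. FL accrual was also expanded after responses had been observed, so the earliest looks may not have happened under the rule. This stands, and it is why the size is given as a range. The bias shrinks but stays positive in every case tried.

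A reader might go further and infer that the planned interval is invalid. It is true that its lower limit is below 20% at 8 of 17 monotherapy pairs and below 39% at 10 of 11 combination pairs. That follows from putting 2.5% in the lower tail against a one-sided 5% rule: a difference in level, not an error. The interval does not under-cover, and at 8/20 its 19.1% is closer to the stage-wise 17.3–17.7% than the rule's own 21.7% is.

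The denominators also matter. Counting non-evaluable subjects as failures lowers the reported ORR, and MZL subjects in Cohort 5 would make it a different statistic from the one monitored. Neither corrects stopping bias.

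An unbiased estimate is not better on every measure. For the combination at 60% the root mean squared error of the UMVUE is 0.142 against 0.134 for the crude proportion. That favours reporting an adjusted figure beside the crude one, not in its place.

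Lastly, ORR is a secondary, preliminary measure in a Phase 1 study, and Section 14.2 lets the SAP modify these plans. The SAP is not in the text available, so it cannot be said that it lacks an adjustment; only that the protocol prescribes none.

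**Conclusion.** The point holds in bounded form. Section 14.9 makes no allowance for the stopping rule of Section 14.1.2. With a stop at first crossing and no overrun, the upward bias at the target rates is 6.8 points (monotherapy) and 3.4 points (combination); under the later-look and overrun assumptions shown it is roughly 2 to 5 and 1 to 2 points. It would be wrong to read 46.8% as what the trial will report at a true 40%.

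The confidence statement is the firmer defect. It belongs to the boundary, not to the interval: 0.05 is a per-look level, and the overall probability of crossing at the null is 0.081 to 0.087 and 0.099 if every listed look is used. A crossing at most of the reachable pairs therefore does not exclude 20% or 39% with 95% confidence once the sequence of looks is counted.

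**What to change.** In Section 14.9 and the SAP, for the FL subjects of Cohorts 1 and 5 and on the evaluable denominator that the boundary uses:

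- keep the crude ORR and its two-sided 95% exact interval;
- add a stopping-adjusted estimate (for example median-unbiased) and a stage-wise one-sided 95% lower bound, both computed from the monitoring and stopping sequence actually followed, including any overrun;
- claim 95% confidence that ORR exceeds 20% or 39% only when that bound does.

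In Section 14.1.2 and the synopsis, describe 0.05 as the per-look level, give the overall crossing probability at each null, and resolve the double entry at N = 11. Adding the adjusted bound alone would not be enough, because it falls below the null at many crossing points; the confidence wording has to change with it.

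The cost is a few sentences, a short program and a record of when each look took place. The reported ORR and the confidence statement become slightly less favourable. The boundaries and the sample size need not change.
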